300 \pm 3.3% \pm 4.7% \pm 5.3% \pm 5.7%

- 2 * Provide the plan for data analysis. Include in the description the types of comparisons that are planned (e.g., comparison of means, comparison of proportions, regressions, analysis of variance, etc.), which is the primary comparison/analysis, and how the analyses proposed will relate to the primary purposes of the study:

From Protocol:

9.I.3. Statistical Analysis

The purpose of this analysis will be to measure the incidence of the CKD-PSIs in the study cohort and to determine the adjusted incidence rates across key factors which relate to safety in CKD. Event ascertainment will begin 4 months (with first telephone follow-up) after enrollment at which time individual events will be recorded longitudinally and cumulatively.

We will consider each specific type of event as an endpoint, but the primary analysis will be based on a composite endpoint of all CKD-PSIs endorsed for inclusion in the trial. The incidence of the events will be expressed per patient-months accrued for all participants in the study cohort and cumulative incidence rates will be determined for both the composite and individual events. Each event will be recorded per individual at the time of the event. For example, if there was an episode of hypoglycemia documented in April for a participant enrolled in January, and an exposure to NSAID in December, then that individual will have 2 CKD-PSI events per 12 patient-months.

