As outlined previously, events will be ascertained from several sources including study visits, medical history review, medication review, and retrieval of hospitalization records. The source of events will be accordingly labeled. Poisson regression will be employed to determine key measured factors which predict the incidence of patient safety events. For this analysis, there will be no predetermined primary exposure to be tested in the regression analysis; however, a key analysis will be the relationship between entry GFR and incidence of CKD-PSIs. Other exposures of interest will be examined. The Poisson regression will assume the number of events for each subject follows a Poisson distribution with mean being a product of the length of the follow-up period and the rate of events, where the logarithm of the expected rate of events (per patient-month), is the linear combination of the covariates. We will check whether data display any over-dispersion and may use negative-binomial regression model if over-dispersion is present.

The data will also be structured such that it is possible to explore the relationship between the incidence of CKD-PSIs and key renal endpoints (secondary outcomes). The key adverse secondary outcomes measures to be examined will be 1) hospitalization and, 2) rate of change in renal function, as measured by estimated GFR. For hospitalization, the primary measure will be incidence of unique hospitalizations over the observed patient-months in each group. Comparisons groups will be the patient-months labeled by the prior incidence or absence of CKD-PSIs in a given patient. While an individual without any CKD-PSI during study observation has a hospitalization, that event occurs in the non-PSI group, another individual with at least one CKD-PSI in the study period who has two hospitalizations – one before and the other after the incidence of the CKD-PSI – will contribute two hospitalization events to the data set. The first will be assigned to the non-CKD-PSI group and corresponding to the period from entry to the occurrence of the first CKD-PSI, the second event will be assigned to CKD-PSI group and corresponding to the period from the occurrence of the first CKD-PSI to last follow up time or the end of the study.

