Generalized estimating equations (GEE) with log link function will be employed for examination of the relationship between incidence of CKD-PSIs and hospitalization. GEE will allow for joint modeling of the repeated measures and the incorporation of such a time-varying covariate based in the detection of a CKD-PSI. The effect of ever experiencing CKD-PSI during the study period on the frequency of hospitalization will be displayed by the rate ratio and its 95% confidence interval of hospitalization in PSI group versus non-PSI group.

Estimated GFR will be determined at baseline and at all annual follow-up visits. Since enrollment will be planned to ensure at least one follow-up visit per individual, it will be possible to generate slope estimates for change in renal function in all study participants. Measurement of serum creatinine will be done at a single laboratory to minimize variation in calibration across laboratories, and GFR will be estimated with the modified MDRD equation. Proper transformation will be performed as needed if the distribution of GFR values is skewed. Random effects models will be used to compare change in GFR between those with and without a CKD-PSI. To employ random effects models as a means to compare change in renal function between those participants with and without the incidence of a CKD-PSI and adjust for multiple covariates, the following assumptions will be made:

Each individual will have a separate slope β_i , with an independent intercept α_i , and an error term ϵ_i with mean 0 and a Normal distribution. The residual variance of each slope is assumed to be the same across all individual slopes and the distribution of β_i for participant time assigned to each group is assumed to be a Normal distribution with a mean of b_1 or b_2 corresponding to the two groups (without or with the bracelet/necklace). Similarly, the distribution of individual intercept α_i is assumed to be a Normal distribution with an equal variance across all individuals, and a mean of a_1 or a_2 corresponding to the two groups.

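### The hospitalization GEE names CKD-PSI status as its only covariate; without entry GFR and time, its rate ratio can differ from 1 when CKD-PSIs have no effect

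*Combined protocol and SAP*

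**What the plan says.** All of this is in section 9.I.3, Statistical Analysis, unless noted.

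- **Hospitalization measure.** "the primary measure will be incidence of unique hospitalizations over the observed patient-months in each group". The groups are defined by person-time: "Comparisons groups will be the patient-months labeled by the prior incidence or absence of CKD-PSIs in a given patient". A patient's non-PSI time is described as "corresponding to the period from entry to the occurrence of the first CKD-PSI"; PSI time runs from there to the end of follow-up.
- **Model.** A GEE with log link, whose one named covariate is PSI status: "the incorporation of such a time-varying covariate based in the detection of a CKD-PSI". No adjustment variable, time term, offset or working correlation is named. The result is presented as the effect of ever having had a CKD-PSI, as a rate ratio with a 95% confidence interval.
- **Adjustment elsewhere.** The aim for PSI incidence is "to determine the adjusted incidence rates across key factors which relate to safety in CKD", and within the Poisson regression "a key analysis will be the relationship between entry GFR and incidence of CKD-PSIs". The random effects model for eGFR is meant to compare the groups "and adjust for multiple covariates, the following assumptions will be made".
- **Dating of PSIs.** "Each event will be recorded per individual at the time of the event". Hospitalization records are one of the sources of PSIs.
- **Data collection (Lay Summary; Study Procedures).** Contacts were six-monthly until July 2016, then one short annual telephone call.

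**The concern.** Of the three regression analyses in the section, only the hospitalization comparison has no stated adjustment. The section itself marks entry GFR as a likely determinant of the exposure. If poorer kidney function also leads to more admissions, it is a confounder.

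Time is a structural problem. Every patient starts in non-PSI time and can only move to PSI time later. Any drift in the admission rate, or in how completely admissions are captured, is therefore attributed in part to PSI status. The plan contains one plausible source of drift, the cut in data collection in July 2016.

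Hospitalization is one of two key secondary outcomes, and the study's overall hypothesis is that CKD-PSIs contribute to adverse events. A ratio that partly reflects kidney function or calendar time could be read as support for that hypothesis, or as evidence against it.

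**Working it through.** The plan gives no admission rate, power or rate ratio for this analysis, so there is no figure to reproduce. The check asks what ratio the described model returns when PSIs have no effect.

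**Inputs.** Section 9.I.4 gives 14.8% with hypoglycemia and 30% with a medication error in a year. These convert to hazards −ln(1 − 0.148) = 0.160 and −ln(1 − 0.30) = 0.357 per year. They are rates for single event types; the composite would be higher. Follow-up of T = 4 years matches the four annual visits planned to June 2016. Assumed, because the documents are silent: 0.5 admissions a year, and the strength of the GFR effects and trends below.

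**Formula.** With independence working correlation, a log person-time offset and PSI status alone, the GEE ratio is the pooled admission rate in PSI time divided by that in non-PSI time. Expected non-PSI time is (1 − e^(−λT))/λ. At λ = 0.357 this is (1 − e^(−1.428))/0.357 = 2.1294 years, leaving 1.8706 years of PSI time.

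**Time trend, no PSI effect.** Let the admission rate be proportional to e^(gt); the base rate cancels. Admissions in non-PSI time are proportional to A = (1 − e^(−(λ−g)T))/(λ − g), and in total to B = (e^(gT) − 1)/g.

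| Trend | g | A | B | Non-PSI rate A/2.1294 | PSI rate (B − A)/1.8706 | Ratio |
|---|---|---|---|---|---|---|
| −20%/yr | ln 0.8 | 1.5544 | 2.6458 | 0.7300 | 0.5834 | 0.80 |
| +10%/yr | ln 1.1 | 2.4798 | 4.8694 | 1.1645 | 1.2775 | 1.10 |

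At λ = 0.160 the same formulas give 0.5734/0.6926 = 0.83 and 1.2864/1.1929 = 1.08. With time in the model, simulation gives 1.00 for both trends.

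**Shared cause, no PSI effect.** As a worked case, take a factor present in half the patients that doubles both rates: PSI hazards 0.24 and 0.48, admission rates 1/3 and 2/3 a year. Non-PSI time is 2.5713 and 1.7779 years; PSI time is 1.4287 and 2.2221 years.

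- Non-PSI rate: (2.5713/3 + 2 × 1.7779/3)/4.3492 = 0.4696.
- PSI rate: (1.4287/3 + 2 × 2.2221/3)/3.6508 = 0.5362.
- Ratio: 0.5362/0.4696 = 1.14. Within each stratum it is 1.00.

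With entry GFR continuous and acting equally on both log rates, simulated GEE fits at N = 350 (independence, robust standard errors) give:

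| GFR effect per SD | Hazard | Unadjusted ratio (lower 95% limit above 1) | With GFR and time |
|---|---|---|---|
| 0.3 | 0.160 | 1.10 (18%) | 1.00 (3%) |
| 0.3 | 0.357 | 1.11 (28%) | 1.00 (3%) |
| 0.5 | 0.160 | 1.30 (79%) | 1.00 (2%) |
| 0.5 | 0.357 | 1.32 (90%) | 1.01 (3%) |

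Numerical integration of the same pooled-rate ratio over a normal GFR score gives 1.10, 1.11, 1.30 and 1.31 for the unadjusted column.

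**Both terms are needed.** With a GFR effect of 0.5 and a 20% yearly fall, the ratio is 1.05 unadjusted, 0.78 with GFR alone and 0.99 with both.

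**Change in capture.** Suppose admissions are constant and follow-up runs to the end of 2021, but only 80% or 60% of admissions are captured after July 2016. The null ratio is then 0.88 to 0.92 or 0.75 to 0.83, over PSI hazards of 0.69 down to 0.16 a year. The capture shares and the 0.69 hazard are assumptions.

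**Dating.** With constant rates, no shared risk and the revealing admission in non-PSI time, detection dating gives a null ratio of 1.00. With a true ratio of 1.5 and time adjusted for, the estimate is 1.51 when PSIs are dated at occurrence, 1.44 when dated at the next six-monthly contact and 1.37 at the next annual one.

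**The case against.** **Covariates may be listed elsewhere.** The text is an extract from a longer protocol that was not supplied, and it does not forbid adjustment. That stands as a limit on what can be claimed. It does not change what the supplied analysis section specifies, which contrasts with the adjustment it states for its other models.

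**The sizes are assumed.** This also stands. No admission rate, trend or GFR effect is given, so only possibility and direction are established.

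**Adjustment may not cure the problem.** Correct for unmeasured severity. With gamma-distributed risk of variance 0.5 shared by PSIs and admissions, the null ratio is 1.63 unadjusted and 1.77 adjusted under independence (1.44 and 1.57 under exchangeable). This is a reason to describe the result as an association; it is not a reason to leave out known, measured factors.

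**Stronger readings that a reader might infer.** One is that the word *detection* sets a second dating rule that itself biases the ratio. The sentence refers back to the rule just described, which splits time at the first PSI's occurrence, and detection dating alone was neutral above. Another is that admissions which reveal a PSI will be counted as PSI time, or dropped, and so inflate the ratio. No part of the plan states either rule, and labelling time by prior PSI points the other way. A third is that admissions triggered by a PSI show null bias. They do not, because such an admission is a consequence of the PSI.

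**Conclusion.** The concern holds for the covariates. As supplied, the hospitalization GEE omits entry GFR and time, and its ratio can move either way from 1 without any PSI effect. Under the assumed rates the departure is roughly 1.1 to 1.3 for GFR confounding, 0.80 for a 20% yearly fall and 1.10 for a 10% yearly rise. All return to about 1.00 with both terms fitted. These figures rest on four years of follow-up, PSI hazards taken from single-event rates, and assumed GFR effects and trends.

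The dating wording is a secondary point. It can place an admission that follows and reveals a PSI in the wrong period, and late dating dilutes a true association, but it does not by itself bias the null ratio.

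The plan should be changed on this point, though the analysis is secondary and exploratory. The documents do not support extending the criticism to the primary composite PSI-incidence analysis.

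**What to change.** 1. In the hospitalization GEE, add entry GFR, time since enrolment with a term for the July 2016 change in data collection, and baseline covariates already collected. State a log person-time offset and robust standard errors. Report the ratio under both independence and exchangeable working correlation; neither need be named as main.
2. Replace detection with the occurrence date used earlier in section 9.I.3. State that an admission during which the first PSI occurs stays in non-PSI time. Add one sensitivity analysis that places every admission whose record reveals the first PSI in non-PSI time.
3. Minor: report the ratio as the association of hospitalization with time after the first CKD-PSI.

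The cost is revised wording and a few extra model runs on data already collected. In the simulations, adjustment changed the standard error by −7% to +17%.

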Name: v2_Lay Summary

View: v2_Justification, Objective, & Research Design

Justification, Objective, & Research Design

If you uploaded a separate research protocol document in the 'Research Protocol' page, cite the applicable section and page numbers from that document in the answer boxes below.

- 1 * Describe the purpose, specific aims, or objectives of this research. State the hypothesis to be tested:

In this study, 371 individuals with pre-dialysis CKD were consented to achieve a cohort of 350 that proceeded to study procedures with the following objectives:

1) Assess the Tolerability and Efficacy of a Commonly-used Medical Alert Accessory Designed to Increase Recognition of Chronic Kidney Disease (CKD) in a Pilot Sample of Participants from the SAFE KIDNEY CARE COHORT

The first 108 subjects of the Safe Kidney Care cohort (Phase I) were provided a medical alert accessory (choice of bracelet or necklace, stainless steel or sterling silver). Regular contacts were made with Phase I participants to monitor tolerance of medical alert accessory along with the use of a supplemental informational website on best safe practices for patients with CKD, and to measure the frequency of newly-developed Patient Safety Indicators specific to CKD (CKD-PSI).

2) Validate Established CKD-PSIs in a Cohort of Individuals with CKD Tracked Longitudinally

After enrollment in Phase I has concluded, an additional 242 volunteers from the target population were enrolled into the Safe Kidney Care cohort (Phase II) for a total of 350 participants tracked longitudinally to detect the incidence of established CKD-PSIs, assess their measurability, and exam the relationship between the occurrence of these safety events and adverse renal outcomes.

- 2 * Discuss the research design including but not limited to such issues as: probability of group assignment, potential for subject to be randomized to placebo group, use of control subjects, etc.:

Study design: Observational cohort study. Study population: Persons with Stage III – V, pre-dialysis CKD enrolled from a single center (n = 350). The first 108 participants (Phase I) were provided a medical alert accessory (choice of bracelet or necklace).

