The random effects model will allow for inclusion of both baseline and time-varying covariates which would include timing of the incidence of the CKD-PSI. In comparison of change in renal function across the two groups (CKD-PSI vs never CKD-PSI), we will test whether the mean slopes b_1 and b_2 are equal, and construct a 95% confidence interval for $d = b_2 - b_1$. For these analyses, we will employ PROC MIXED in SAS V9.1 (SAS Institute Inc., Cary, NC, USA), building on the research group's substantial prior experience using such models and examining changes in renal function.

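### The 95% interval for the slope difference d can be miscalibrated: the random effects model assumes an independent intercept and common variances, and names no check or robust standard error

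*Combined protocol and SAP*

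**What the plan says.** The text is in Sample Size and Data Analysis, item 2, which reproduces protocol section 9.I.3 (Statistical Analysis). Each participant has an own slope "with an independent intercept". On variances, the plan says "The residual variance of each slope is assumed to be the same across all individual slopes", and that the individual intercept "is assumed to be a Normal distribution with an equal variance across all individuals". The slope distribution, "for participant time assigned to each group is assumed to be a Normal distribution with a mean of b_1 or b_2", has group-specific means; nothing is said about whether its variance may differ between groups.

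The means are labelled as "corresponding to the two groups (without or with the bracelet/necklace"). The test is described differently: "In comparison of change in renal function across the two groups (CKD-PSI vs never CKD-PSI"). For that test the plan will "construct a 95% confidence interval for" d = `b_2` − `b_1`, using PROC MIXED. Rate of change in eGFR is a secondary outcome. Apart from transforming skewed GFR values, the plan describes no check of these assumptions and no fallback.

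**The concern.** If one slope variance is estimated for both groups, the standard error of d borrows variability from one group to describe the other. When the groups are of unequal size and unequal variability, that standard error is wrong. The interval is too narrow if the smaller group is the more variable one, and too wide if the larger group is.

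The independence assumption raises a separate question. The cohort has Stage III-V CKD, with ESRD and death among the outcomes, so some eGFR series may end early at low values. The plan also treats entry GFR as a key correlate of CKD-PSI incidence, so the two groups may start at different levels. In that setting, forcing zero covariance between intercept and slope can move the estimate of d as well as its standard error.

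The same section protects its event-count model, with an over-dispersion check and a negative-binomial alternative. The slope model has no comparable safeguard.

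**Working it through.** The plan gives no SD, power or interval width for the slope comparison, so there is no stated figure to reproduce.

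**1. Inputs.** From the documents: 350 participants ("for a total of 350 participants tracked longitudinally"), a 95% interval, and baseline plus up to 4 annual visits, taken here as 5 eGFR values at years 0 to 4. Assumed: slope SD 4 per year (CKD-PSI) and 2.5 (never), residual SD 4, each participant counted in one group.

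**2. Variance of one participant's slope.** v = slope SD² + residual SD²/Sxx, with Sxx = 4 + 1 + 0 + 1 + 4 = 10.
- CKD-PSI: v1 = 16 + 16/10 = 17.6
- Never: v0 = 6.25 + 1.6 = 7.85

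**3. Coverage.**
- True Var(d) = v1/n1 + v0/n0.
- With one pooled variance, the model reports v̄(1/n1 + 1/n0), where v̄ = (n1·v1 + n0·v0)/350.
- Coverage = 2Φ(1.96 × model SE / true SE) − 1.

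For an 87/263 split: v̄ = (87 × 17.6 + 263 × 7.85)/350 = 10.27. Model variance = 10.27 × (1/87 + 1/263) = 0.157. True variance = 17.6/87 + 7.85/263 = 0.232. SE ratio = √(0.157/0.232) = 0.82.

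| CKD-PSI share | Model SE | True SE | Ratio | Coverage |
|---|---|---|---|---|
| 25% (87/263) | 0.396 | 0.482 | 0.82 | 89% |
| 47% | 0.378 | 0.386 | 0.98 | 94.5% |
| 50% | 0.381 | 0.381 | 1.00 | 95% |
| 75% (263/87) | 0.482 | 0.396 | 1.22 | 98% |
| 76% | 0.489 | 0.399 | 1.22 | 98.4% |

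**4. Which share is plausible?** The sample size section gives annual proportions of 14.8% (hypoglycemia) to 30% (medication error). If these are constant and independent over 4 years (an assumption), the share ever affected is 1 − 0.852⁴ = 47% to 1 − 0.70⁴ = 76% for a single event type. The 10% to 40% range of Table 4 gives 1 − 0.9⁴ = 34% to 1 − 0.6⁴ = 87%. A composite raises the share; repeat events in the same people lower it.

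**5. Other variance inputs.** A large-sample calculation fitted the common-variance model to data with unequal slope SDs. Assumptions: never-group slope SD 2 or 3, residual SD 4 or 6, CKD-PSI slope SD 1.5 or 2 times larger, and either 5 visits for all or an equal mix of 2 to 5. Coverage was 83-92% at a 20-30% share, 95% at 50%, and 97% to 99.5% at 70-80%. Unequal residual SD alone (1.5 or 2 times) gave 92.5% or 89.8% at a 20% share, 95% at 50%, and 96.8% or 97.9% at 80%.

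**6. Zero intercept-slope covariance.** With equal variances and visit patterns unrelated to eGFR, true correlations of −0.5 to 0.5 gave coverage of 93.7% to 95.8%; an unstructured covariance restored 95.0%.

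With stopping that depends on eGFR, a simulation used 250 datasets per setting, n = 350, a 40% CKD-PSI share, 2 to 5 visits and series ended after eGFR below 15. CKD-PSI baseline was 6 mL/min lower, intercept SD 12, slope SD 3, residual SD 4, and true d = 0. Mean estimates of d:

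| Correlation | Independent | Unstructured | Shift |
|---|---|---|---|
| −0.5 | −0.166 | 0.021 | −0.187 |
| −0.3 | −0.157 | −0.054 | −0.103 |
| 0.3 | 0.094 | −0.008 | 0.102 |
| 0.5 | 0.203 | 0.043 | 0.160 |

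A second set of runs gave shifts of 0.08 to 0.13, and none when the groups started at the same eGFR. Against an SE of about 0.45, a shift of 0.1 is 0.1/0.45 = 0.22 SE; the largest, 0.187, is 0.42 SE.

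**The case against.** The strongest reply is that these are ordinary mixed-model assumptions in a secondary, partly exploratory analysis, and that nothing in the documents shows them to be false. All the SDs above are assumed. That stands, and it limits the point to a recommended safeguard.

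The wording also supports less than it first appears to. The sentence on residual variance most naturally describes scatter around each person's line, whereas more variable decline concerns the spread of slopes between people. Equal variance is stated expressly only for intercepts. Pooling of the slope variance is implied, because only the means differ by group and a default PROC MIXED random statement estimates one covariance. Likewise, "with an independent intercept" most naturally means zero intercept-slope covariance, but could mean only that each person has an own intercept.

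A reader might infer that the interval is wrong whenever CKD-PSI participants decline more variably. It is not: with equal groups, coverage is nominal. Undercoverage needs CKD-PSI participants to be a more variable minority, and the plan's annual rates point the other way, although a minority cannot be excluded. A reader might also infer that early-ending series bias d in general. In the runs, that needed correlated intercept and slope, different starting eGFR, and stopping at low eGFR, all together.

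**Conclusion.** The point holds as a minor one. The plan states restrictive covariance assumptions for the slope model, and the interval for d has no protection if they fail. Under the assumed SDs of 4, 2.5 and 4, coverage runs from about 89% (25% CKD-PSI share) through about 94-95% (near 50%) to about 98% (75%). At the 47-76% shares implied by the plan's single-event rates it is 94.5% to 98.4%, so the likelier consequence is a near-nominal or somewhat wide interval. The shift in d from imposing zero covariance is roughly 0.1 mL/min/yr, conditional on assumed inputs, and small beside its SE. The documents do not support saying that the planned interval is invalid. The mismatch between the bracelet/necklace labels and the CKD-PSI comparison is plain in the text and rests on no assumption.

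**What to change.** In section 9.I.3:

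- Replace the independent intercept by an unstructured intercept-slope covariance (RANDOM INTERCEPT TIME / TYPE=UN).
- Base the 95% interval for d on empirical (sandwich) standard errors.
- Add a sensitivity analysis with variances estimated separately by CKD-PSI group, where the model converges.
- Relabel `b_1` and `b_2`, and the intercept means, so that the groups defined in the model are the groups tested.

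The cost is a line or two of text, a few PROC MIXED options and one extra covariance parameter. The group-specific form may sometimes fail to converge, since some participants may contribute only two eGFR values; the empirical standard errors then remain. These correct the stated precision but not any shift in the estimate of d, so the unstructured covariance is needed as well.

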Mod 11 Changes to be initiated July 1, 2016: Participants will no longer need to retain medication containers/packaging; attend an annual follow-up clinic visit; wear the medical alert bracelet/necklace, or maintain a diary.

ID: VIEW4E0280585B400
Name: v2_Study Procedures

Sample Size and Data Analysis

If you uploaded a separate research protocol document in the 'Research Protocol' page, cite the applicable section and page numbers from that document in the answer boxes below.

- 1 * Provide the rationale and sample size calculations for the proposed target population:

From PI's Protocol, Section 9.I.4, page 30:

9.I.4. Sample Size Considerations

For this study, the key aim of the power calculations will be to ensure adequate precision in the detected estimates of CKD-PSIs. In order to conduct such power calculations it is important to make reliable assumptions about the expected incidence rate of key disease-specific safety indicators.

The preliminary data presented offers evidence of the expected incidence rate of selected events. The estimated incidence of various CKD-specific safety events reported by PI range from 14.8% of participants, with an episode of hypoglycemia (glucose \leq 60 mg/dl) in a given year, to 30% with a medication error in a given year. When considering a composite of a series of prospective, disease-specific safety indicators, one can see that the expected incidence rate could be substantial. Yet, to determine the precision of incidence estimates of CKD-PSIs in the validation cohort, we varied the presumed baseline rate from a conservative low frequency to a range closer to what is suggested by our preliminary data (Table 4 on page 31 of PI's protocol and below). Choosing the sample size for Phase II cohort of 250 (final n 242), achieved confidence interval, across our projections for a baseline incidence rate, assures a high degree of precision in measured event rates for CKD-PSIs.

The additional sample of 110 (final n 108) participants for piloting the medical alert accessory (Phase 1) will provide a reasonable estimate of the acceptance and tolerability of the alert accessory.

Table 4

Precision (95% Confidence interval for varying baseline incidence of safety indicators and different sample sizes)

Baseline incidence rate per year of (CKD-PSIs)

Sample size 10% 20% 30% 40%

100 \pm 6% \pm 8% \pm 9% \pm 10%

200 \pm 4% \pm 5.5% \pm 6.5% \pm 7%

250 \pm 3.6% \pm 4.8% \pm 5.6% \pm 6%

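### The eGFR slope means in 9.I.3 are defined by bracelet/necklace but tested by CKD-PSI status, with the grouping unit and the sign of d left open; study phase is also not named in the CKD-PSI rate analysis

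*Combined protocol and SAP*

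**What the plan says.** All references are to the Combined protocol and SAP.

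**eGFR slopes (9.I.3 Statistical Analysis).** The aim is stated as "Random effects models will be used to compare change in GFR between those with and without a CKD-PSI". The model assumptions then give each participant a slope and an intercept. For follow-up time allotted to each group, the slopes are Normal "with a mean of b_1 or b_2 corresponding to the two groups (without or with the bracelet/necklace"; the intercept means a_1 and a_2 refer to the same two groups. The final paragraph allows time-varying covariates, including when the CKD-PSI occurred. It then says that, "across the two groups (CKD-PSI vs never CKD-PSI), we will test whether the mean slopes" b_1 and b_2 are equal, with a 95% confidence interval for d = b_2 − b_1.

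**CKD-PSI rate (9.I.3 and 9.I.4).** "The incidence of the events will be expressed per patient-months accrued for all participants in the study cohort". The Poisson model names entry GFR and leaves other exposures open. The precision argument in 9.I.4 is made for one phase: "Choosing the sample size for Phase II cohort of 250 (final n 242), achieved confidence interval". The Phase I sample is justified because it "will provide a reasonable estimate of the acceptance and tolerability of the alert accessory".

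**Objective 1 (Justification, Objective, & Research Design, item 1).** The title is "Assess the Tolerability and Efficacy of a Commonly-used Medical Alert Accessory". The text below it says that Phase I contacts serve, among other things, "to measure the frequency of newly-developed Patient Safety Indicators specific to CKD (CKD-PSI".

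**The concern.** Change in renal function is one of two key secondary outcomes in 9.I.3. If the parameters being tested are defined by one grouping and tested by another, an analyst who follows the text literally can fit the wrong contrast. One who corrects it by judgement must still choose which group is b_1 and whether a participant changes group at the first CKD-PSI. Those choices should not be made after the data are seen.

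The unit of grouping matters more than the label. If participants are classed as ever or never, eGFR measured before a CKD-PSI counts towards the CKD-PSI group, and longer follow-up gives more chance of entering it. If follow-up time is classed, earlier eGFR stays in the group without a prior event. These are different estimands.

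On the rate, the accessory is the one procedural difference that the Lay Summary gives between the phases. A pooled rate without rates by phase hides how far it depends on the mix. An efficacy statement with no planned analysis would rest on a non-randomised comparison of consecutive enrolment phases.

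**Working it through.** **1. Group definitions set side by side (9.I.3).**
- Aim of the eGFR model: with or without a CKD-PSI.
- Definition of b_1/b_2 and a_1/a_2: without or with the accessory, by participant follow-up time.
- Test of b_1 = b_2: CKD-PSI or never CKD-PSI, which reads as a grouping of persons.
- Hospitalisation analysis, for comparison: time from entry to the first CKD-PSI is one group, and time after it is the other.

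The aim and the test agree on CKD-PSI status; only the definition differs. The definition orders the groups without/with and the test orders them CKD-PSI/never. If b_1 follows the first order, d is with minus without. If it follows the second, the sign reverses.

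**2. Do the two labels pick out different people?** By accessory the split is 108 and 242. By CKD-PSI status it depends on the yearly risk p. Assume constant p, no attrition, and uniform enrolment from January 2011 to December 2014 (Study Procedures, item 3, gives only the years). Follow-up T to 30 June 2016 then runs from 1.5 to 5.5 years. The proportion ever affected is the mean of 1 − (1 − p)^T:
- p = 0.10: 1 − (0.9^1.5 − 0.9^5.5)/(4 × 0.1054) = 0.30, or 106 of 350.
- p = 0.40: 1 − (0.6^1.5 − 0.6^5.5)/(4 × 0.5108) = 0.80, or 281 of 350.

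Even where the counts are close, the members differ.

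**3. The plan's own precision.** For n = 250, 1.96 × √(p(1 − p)/n) gives ±3.72, ±4.96, ±5.68 and ±6.07 points at 10, 20, 30 and 40%. Table 4 gives ±3.6, ±4.8, ±5.6 and ±6, so agreement is within 0.16 points. The same formula at 30%:
- Phase I, n = 108: ±8.6 points.
- Phase II, n = 242: ±5.8 points.
- Both, n = 350: ±4.8 points.

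**4. How much could pooling move the rate?** The documents give no accessory effect, so this is illustration only. If the Phase I rate is RR times the Phase II rate, the pooled rate differs from the Phase II rate by w(1 − RR), where w is the Phase I share of follow-up. With enrolment as in step 2 and Phase I enrolled first:
- Phase I: 108 × 4.88 = 527 patient-years.
- Phase II: 242 × 2.88 = 698 patient-years.
- w = 527/1225 = 0.43 (by headcount, 108/350 = 0.31).

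At a Phase II rate of 30 events per 100 patient-years, with Poisson half-width 1.96 × √(pooled rate/1225):
- RR 1: no shift.
- RR 0.8: shift 30 × 0.43 × 0.2 = 2.6 per 100 patient-years; half-width 2.9.
- RR 0.5: shift 30 × 0.43 × 0.5 = 6.5; half-width 2.7.

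Nothing in the documents supports any particular RR.

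**5. Efficacy.** The Lay Summary, the outcomes paragraph, the rationale and 9.I.4 state the accessory aim as acceptability, or acceptance and tolerance. The Lay Summary and Objective 1 also foresee measuring CKD-PSI in Phase I. No comparator or phase contrast appears in the supplied text.

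**The case against.** The strongest reply is that the intended slope contrast is not in doubt. The aim and the test both name CKD-PSI, so the accessory label is a slip in one parenthesis. That is right about intent. A reader might infer that the study plans to compare eGFR decline by accessory; no other sentence supports this. It is also true that neither the equality test nor the interval width depends on the sign of d, and that the without/with order hints at a direction. What stands is that the parenthesis is the only definition of the tested parameters, and that correcting the label alone does not settle persons against follow-up time.

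On pooling, the reply is that Objective 2 asks for incidence in all 350 participants, and that 350 gives more precision than the Phase II sample argued for in 9.I.4. The stated purpose of 9.I.3 includes adjusted rates across factors related to safety, and other exposures may be examined. All of this stands. A reader might infer that the pooled rate is invalid, that a Phase II rate is ruled out, or that the study's own hypothesis puts the pooled rate too low. The documents support none of these. The overall hypothesis links poor recognition to more CKD-PSI, and the accessory is intended to raise recognition, but no effect of the accessory on CKD-PSI is hypothesised.

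On efficacy, the word stands in one title, and 9.I.3 and 9.I.4 are extracts of a longer protocol. It cannot be said that the full protocol lacks an efficacy analysis.

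**Conclusion.** The main point holds: the eGFR parameters in 9.I.3 are wrongly labelled as written, d has no fixed sign, and the unit of grouping is inconsistent. This rests on the text alone, with no numerical assumption. It affects a key secondary analysis, and wording can repair it.

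The point on phase is smaller. Pooling is legitimate and a phase term is allowed; what is missing is that phase is named. Any numerical effect of pooling is unknown, and the figures in step 4 depend on assumed rate ratios and enrolment. The point on efficacy is minor and limited to the supplied text. Overall: minor to moderate.

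**What to change.** 1. **eGFR model.** In 9.I.3 replace the bracelet/necklace label with CKD-PSI status. Define b_1 (a_1) as follow-up without a prior CKD-PSI and b_2 (a_2) as follow-up after the first CKD-PSI, as in the hospitalisation analysis, so that d is after minus before. Amend the CKD-PSI/never wording of the test to match. Since a participant can then belong to both groups in turn, say that the mean slope changes at the first CKD-PSI. The cost is wording and one stated model term. Because eGFR comes from baseline and annual visits, some participants will have few values on one side of the event.

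2. **CKD-PSI rate.** Keep the pooled primary rate. Beside it, report the composite rate for Phase I and for Phase II, with a pooled rate over the same window: follow-up before 1 July 2016, when clinic visits stopped and accessory wear was no longer required. Include phase as a covariate in the Poisson or negative-binomial model over that window, described as confounded with enrolment period and not as a device effect. Similar rates would not show that the accessory has no effect, since a period trend could offset one. The cost is a covariate already recorded. Rates by phase are less precise (step 3), and patient-months after June 2016 are not used in the by-phase comparison. The primary estimate is unchanged.

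3. **Objective 1.** Drop efficacy from the title, or label any Phase I to Phase II rate ratio as exploratory and non-randomised. With the patient-years in step 4 and an assumed 0.3 events per patient-year in both phases (158 and 209 events), its 95% interval would be exp(1.96 × √(1/158 + 1/209)), that is ×/÷ 1.23, or ×/÷ 1.34 with the variance doubled for over-dispersion.
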